## **11. LEGAL/ETHICS and ADMINISTRATIVE PROCEDURES**

### **11.1. Good Clinical Practice/Regulatory Compliance**

The procedures set out in this study protocol, pertaining the conduct, evaluation, and documentation of this study, are designed to ensure that the Sponsor and Investigators abide by the Declaration of Helsinki, Good Clinical Practice (GCP) and International Council for Harmonisation (ICH).

It is the Investigator's responsibility to ensure that adequate time and appropriate resources are available at the study site prior to commitment to participate in this study. The Investigator should also be able to estimate or demonstrate the potential for recruiting the required number of suitable patients within the agreed recruitment period. The Investigator will maintain a list of appropriately qualified person to whom the Investigator has delegated significant study-related tasks.

### **11.2. Study Site and Investigator Qualification**

This study will be performed by appropriately qualified and licensed Investigators at two sites in the UK. All site staff must be appropriately qualified by education, training and experience to perform the study related duties allocated to them, which must be recorded on the site delegation log.

GCP training is required for all staff responsible for study activities. The frequency of repeat training may be dictated by the requirements of their employing institution, or 2 yearly where the institution has no policy, and more frequently when there have been updates to the legal or regulatory requirements for the conduct of clinical trials.

The study sites will be reviewed by UCL CTC (on behalf of the Sponsor) to verify that they are able to conduct the study.

#### **11.2.1. Investigator Curriculum Vitae (CV)**

The Investigator will provide the Sponsor or designee with his/her current curriculum vitae (CV), and any revisions/updates, as well as those of any sub-investigator or staff personnel with significant study responsibilities.

#### **11.2.2. Site qualifications and study-specific procedural training**

The Institution must have appropriately qualified Investigators, and clinical and administrative support staff in place to adequately conduct the study according to GCP in general and must have the adequate expertise and staff to conduct this study in compliance with the relevant guidelines and regulations and to treat patients with HCC and mCRC.

The physicians who will perform the treatment with BTG-002814 will be qualified Interventional Radiologists who are experienced with DEB-TACE treatments and will be accustomed to DC Bead® and its comparator products as spherical microsphere embolisation devices. However, prior to performing the first study-related treatment, the Interventional Radiologists who will be performing the treatment will undergo documented training in the use of RO bead.

### **11.2.3. Laboratory Certification and Normal Values**

The Investigator will provide the Sponsor with the name and location of the clinical laboratory to be used for determination of laboratory assays, copy of certification, and a list of the normal range of values of all laboratory tests. Any changes in laboratory, certification or normal ranges will be communicated promptly to the Sponsor or UCL CTC.

## **11.3. Institutional Review Board (IRB)/Independent Ethics Committees (IEC)**

### **11.3.1. Institutional Approval of the Protocol**

It is the responsibility of UCL CTC to submit this protocol, the informed consent document (approved by the Sponsor or designee), relevant supporting information and all types of patient recruitment information to the Research Ethics Committee (REC) for review and approval prior to site initiation. A copy of the written approval of the protocol and ICF must be received by the Sponsor or designee prior to shipment of investigational product or recruitment of patients. Prior to implementing changes in the study, the Sponsor and REC must also approve any revised informed consent documents and amendments to the protocol with documentation of the approvals submitted to the Sponsor or designee. The approval document should clearly state the study reference, date of review and actions taken.

The Sponsor or designee will be responsible for keeping the REC apprised of the progress of the study, any changes to the protocol, deviations from the protocol and SAEs as required by the REC.

### **11.3.2. IRB/Ethics Committee Membership Roster**

A complete and current membership roster of the REC should be provided to the Sponsor or designee.

## **11.4. Informed Consent**

It is the responsibility of the Investigator to obtain written Informed Consent from patients prior to the conduct of any study procedures. All Informed Consent documentation must be in accordance with applicable regulations and GCP. Each patient is requested to sign the ICF after the patient has received and read the written information and received an explanation of the study, including but not limited to: the objectives, treatment plan, potential benefits and risk, inconveniences, alternative treatment options and the patient's rights and responsibilities. A copy of the Informed Consent documentation (Informed Consent Form or Patient Information and Informed Consent Form, as applicable) must be given to the patient or the patient's legally authorised representative.

Acquisition of the Informed Consent should be documented in the patient's medical record and the ICF should be personally signed and dated by the patient and the individual who conducted the Informed Consent discussion. Signed Informed Consent forms must remain in each patient's study file and must be available for verification by Study Monitors at any time.

The Sponsor must receive a copy of the REC- approved Informed Consent form and a copy of the REC written approval, prior to the start of the study. Additionally, if the REC required modification of the sample Patient Information and Informed Consent document provided by the Sponsor, the documentation supporting this requirement must be provided to the Sponsor.

The Sponsor reserves the right to delay initiation of the study at a site where the Informed Consent forms do not meet the standards of applicable regulations and international GCP standards/guidelines.

## 11.5. Patient Privacy and Confidentiality

The Sponsor and Investigator affirm and uphold the principle for the patient's right to protection against invasion of privacy. Throughout this trial, all data collected and analysed by the Sponsor or designee will be treated confidentially and identified by an identification number.

To verify compliance with the protocol, the Sponsor will require the Investigator to permit its designee access to the patient's primary medical record to review those portions that directly concern this study (including but not limited to laboratory test results, radiology images, and hospital and outpatient records).

As part of required content of the Informed Consent, the patient must be informed that his/her records will be reviewed by the Sponsor, Sponsor representative and/or a representative of the appropriate competent authority and Safety Committee. The Informed Consent or related document will also state that patient privacy will be maintained pursuant to local regulations. Should access to such medical records require a waiver or authorisation separate from the statement of Informed Consent, the Investigator will obtain such permission in writing from the patient before the patient is entered in the study.

Patient identifiable data, including initials, gender and age, will be required for the registration process and will be provided to UCL CTC. UCL CTC and the Sponsor will preserve patient confidentiality and will not disclose or reproduce any information by which patients could be identified. Data will be stored in a secure manner and studies conducted by UCL CTC are registered in accordance with the Data Protection Act 1998 with the Data Protection Officer at UCL.

Data collected during this study may be used to support the development, registration or marketing of BTG-002814. Collected data may be reviewed by the Sponsor and/or its representatives, independent auditors who validate the data on behalf of the Sponsor, third parties with whom the Sponsor may develop, register or market BTG-002814, national or local competent authorities and the REC which granted approval for this study to proceed.

## 11.6. Study Monitoring

Monitoring of the study will be detailed in the Study Monitoring Plan and will be performed by qualified personnel from the Sponsor or Sponsor designee. At the monitoring visits, the progress of the study will be discussed with the Investigator or his/her representative. The ICFs will be reviewed for signatures and the CRFs checked for completeness and accuracy. Patient source data must be available for review. The Investigator and his/her staff are expected to cooperate with the Study Monitor and be available during at least a portion of the monitoring visit to review the CRFs and any queries/resolutions, answer questions, and provide any missing information.

The Study Monitor will record the date of each visit together with a summary of the status and progress of the study. Proposed actions will be confirmed with the Investigator in writing. Telephone and electronic mail contact will be made with the Investigator and study staff as necessary during the data collection and report writing periods.

## 11.7. Modification of the Protocol

UCL CTC (on behalf of the Sponsor) will be responsible for gaining ethical and regulatory approval(s), as appropriate, for amendments made to the protocol and other study-related documents. Once approved, UCL CTC will ensure that all amended documents are distributed to sites as appropriate.

Site staff will be responsible for acknowledging receipt of documents and for implementing all amendments promptly.

All amendments to the protocol must be documented in writing, reviewed and approved by the Chief Investigator and Sponsor and submitted to the REC and/or competent authority for approval prior to initiation. If the protocol amendment substantially alters the study design or potential risk to the patient, new written Informed Consent must be obtained from each patient for continued participation in the study.

## 11.8. Suspension or Termination of Study

If conditions arise requiring further clarification before the decision can be reached to proceed with or terminate the study, the study will be suspended until the situation has been resolved.

The Sponsor has the right to terminate this study and remove all study material from the site at any time. Examples of situations where this might occur include:

- It becomes apparent that patient enrollment is unsatisfactory with respect to quality and/or quantity or data recording is chronically inaccurate and/or incomplete.
- The incidence and/or severity of adverse events in the study indicate a potential health hazard caused by the trial treatment.

## 11.9. Departure from Protocol

No deviation may be made from the protocol unless an amendment has been agreed to in writing by both the Investigator and the Sponsor and approved by the REC and competent authority, if applicable. When an emergency occurs that requires a departure from the protocol for an individual, the Investigator or other physician in attendance will, if circumstances and time permit, contact UCL CTC or their representatives, immediately by telephone. Urgency is important to permit a decision as to whether or not the patient (for whom the departure from protocol effects) is to continue in the study. The source documents will completely describe the departure from the protocol and state the reasons for such departure. As appropriate, the REC will be notified in writing.

Urgent Safety Measures will be reported to the MHRA in accordance with the MHRA guidance on Reporting Urgent Safety Issues

### 11.9.1. Protocol Deviations

All protocol deviations will be documented and will be reviewed periodically by the Sponsor as detailed in the study Protocol Deviation Plan.

Protocol deviations will be tracked according to the following categories:

- Informed consent process not followed
- Screening tests or procedures out of window or not done
- Imaging tests not performed as required

- Dose delivery outside specified range □ Use of prohibited medications

Major protocol deviations are defined as:

- Enrollment violations: eligibility criteria deviations, informed consent issues,
- Data violations: those affecting primary study endpoints All others will be classified as minor protocol deviations

### 11.9.2. Serious Breaches

A “serious breach” is defined as a breach of the protocol or of the conditions or principles of Good Clinical Practice which is likely to affect to a significant degree the safety or physical or mental integrity of the trial subjects, or the scientific value of the research.

Systematic or persistent non-compliance by a site with GCP and/or the protocol, including failure to report SAEs occurring on trial within the specified timeframe, may be deemed a serious breach.

In cases where a serious breach has been identified, BTG will inform the MHRA and REC within 7 calendar days of becoming aware of the breach.

## 11.10. Recording, Access to and Retention of Source Data

Investigators are required to prepare and maintain adequate source documentation which includes:

- Documents relative to the patient medical history that verify Eligibility criteria
- Records covering patient participation in the study including basic identification information, results of physical examinations and diagnostic tests, original laboratory results (initialled and dated by the Investigator), study treatment administration, concurrent medication information, and visit notes.

Data must be recorded in the patient’s source documents including the date of Informed Consent.

The Investigator must permit authorised representatives of the Sponsor, the competent authority, the REC, and auditors to inspect facilities and records relevant to the study.

The monitor, auditors, REC or regulatory inspectors may check the CRF entries against the source documents. The Informed Consent form will include a statement by which the patients allow the above-named access to source data that substantiate information recorded in the CRFs. These personnel, bound by professional secrecy, will not disclose any personal information or personal medical information.

As described in the ICH GCP Guidelines, ‘essential documents’, including CRFs, source documents, Informed Consent forms, laboratory test results, IP inventory records, should be retained by the Investigator until at least two years after the last approval of a marketing application in an ICH region or at least two years have elapsed since the formal discontinuation of a clinical development of the IP. These documents should be retained for a longer period however if required by the applicable regulatory requirements or by an agreement with the Sponsor. The Investigator must obtain written permission from the Sponsor prior to destruction of any study document.

These records must be made available at reasonable times for inspection and duplication, if required.

## 11.11. Source Documents and Case Report Forms

The Investigator is responsible for maintaining adequate and accurate source documents from which accurate information will be transcribed into CRFs that have been designed to capture all observations and other data pertinent to the clinical investigation. CRFs should be completed by the Investigator or delegate as stated on the Delegation of Authority Log.

Overwriting of information or use of liquid correcting fluid is not allowed in source documentation. Once the Study Monitor has verified the contents of the completed CRF against the source data, queries may be raised if the data are unclear or contradictory.

## 11.12. End of Study

For regulatory purposes the end of the study will be the last visit of the last subject (LVLS), at which point the 'declaration of end of trial' form will be submitted to the MHRA and Ethics Committee, as required.

Following this, UCL CTC will advise sites on the procedure for closing the study at the site.

Once the end of study has been declared, no more prospective patient data will be collected but sites must co-operate with any data queries regarding existing data to allow for analysis and publication of results.

## 11.13. Publications

All manuscripts, abstracts or other modes of presentation arising from the results of the study will be prepared by the Chief Investigator and must be reviewed and approved in writing by the Sponsor, in advance of submission. The review is intended to protect Sponsor proprietary information existing either at the date of commencement of the study or generated during the study. No individual Investigator may publish results from his/her site until after publication of the primary manuscript describing the full study population.

The detailed obligations regarding the publication of any data, material results or other information that is generated or created in relation to the study shall be set out in the agreement between the Investigator and Sponsor.

In accordance with recommendations from the International Committee of Medical Journal Editors, the study will be listed in a publicly accessible registry of clinical trials such as [clinicaltrials.gov](http://clinicaltrials.gov).

## 11.14. Audit/Inspections

BTG Clinical Quality Assurance may audit the study sites at any time during the study. To ensure compliance with relevant regulations, data generated by this trial must be available for inspection upon request by representatives of the REC, competent authorities, the Sponsor and its representatives.

## Appendix 1. Medications Known to Prolong QT Interval and/or Induce Torsades de Pointes

**Table 3. Drugs that are generally accepted by authorities to have a risk of causing Torsades de Pointes (TDP)**

Drug (Generic Names)	Drug Class (Clinical Usage)	Comments
Amiodarone	Anti-arrhythmic/abnormal heart rhythm	TDP risk regarded as low
Arsenic trioxide	Anti-cancer/Leukaemia	
Astemizole	Antihistamine/Allergic rhinitis	
Azithromycin	Antibiotic/bacterial infection	
Bepridil	Anti-anginal/heart pain	
Chloroquine	Anti-malarial/malaria infection	

Chlorpromazine	Anti- psychotic/Antiemetic/schizophrenia/nausea	
Cisapride	GI stimulant/heartburn	
Citalopram	Anti-depressant/depression	
Clarithromycin	Antibiotic/bacterial infection	
Disopyramide	Anti-arrhythmic/abnormal heart rhythm	
Dofetilide	Anti-arrhythmic/abnormal heart rhythm	
Domperidone	Anti-nausea/nausea	
Droperidol	Sedative; Anti-nausea/anesthesia adjunct, nausea	
Erythromycin	Antibiotic; GI stimulant/bacterial infection; increase GI motility	
Escitalopram	Anti-depressant/Major depression/Anxiety disorders	
Flecainide	Anti-arrhythmic/abnormal heart rhythm	
Halofantrine	Anti-malarial/malaria infection	
Haloperidol	Anti-psychotic/schizophrenia, agitation	TDS risk with IV or excess dosage
Ibutilide	Anti-arrhythmic/abnormal heart rhythm	
Levomethadyl	Opiate agonist/pain control, narcotic dependence	
Mesoridazine	Anti-psychotic/schizophrenia	
Drug (Generic Names)	Drug Class (Clinical Usage)	Comments
Methadone	Opiate agonist/pain control, narcotic dependence	
Moxifloxacin	Antibiotic/bacterial infection	
Pentamidine	Anti-infective/pneumocystis pneumonia	
Pimozide	Anti-psychotic/Tourette's tics	
Probucol	Antilipemic/Hypercholesterolemia	
Procainamide	Anti-arrhythmic/abnormal heart rhythm	

Quinidine	Anti-arrhythmic/abnormal heart rhythm	
Sevoflurane	Anesthetic, general/anaesthesia	Label warning for patients with congenital long QT or patients taking QT prolonging drugs
Sotalol	Anti-arrhythmic/abnormal heart rhythm	
Sparfloxacin	Antibiotic/bacterial infection	
Terfenadine	Antihistamine/Allergic rhinitis	
Thioridazine	Anti-psychotic/schizophrenia	
Vandetanib*	Anti-cancer/Thyroid cancer	*Does not apply to this study

**Table 4. Drugs that in some reports may be associated with Torsades de Pointes but at this time lack substantial evidence of causing Torsades de Pointes**

Drug (Generic Names)	Drug Class (Clinical Usage)	Comments
Alfuzosin	Alpha1-blocker/Benign prostatic hyperplasia	
Amantadine	Dopaminergic/Anti-viral/Anti-infective/Parkinson's Disease	
Arteminol + Piperaquine	Anti-malarial	
Atazanavir	Protease inhibitor/HIV	
Bedaquiline	Anti-infective/Drug-resistant Tuberculosis	
Chloral hydrate	Sedative/sedation/insomnia	
Clozapine	Anti-psychotic/schizophrenia	
Dolasetron	Anti-nausea/nausea, vomiting	
Dronedarone	Anti-arrhythmic/Atrial Fibrillation	
Eribulin	Anti-cancer/metastatic breast neoplasias	
Famotidine	H2-receptor antagonist/Peptic ulcer/GERD	
Felbamate	Anti-convulsant/seizure	

Drug (Generic Names)	Drug Class (Clinical Usage)	Comments
Fingolimod	Immunosuppressant/Multiple Sclerosis	

Foscarnet	Anti-viral/HIV infection	
Fosphenytoin	Anti-convulsant/seizure	
Gatifloxacin	Antibiotic/bacterial infection	
Gemifloxacin	Antibiotic/bacterial infection	
Granisetron	Anti-nausea/nausea and vomiting	
Iloperidone	Antipsychotic, atypical/Schizophrenia	
Indapamide	Diuretic/stimulate urine & salt loss	
Isradipine	Anti-hypertensive/high blood pressure	
Lapatinib	Anti-cancer/breast cancer, metastatic	
Levofloxacin	Antibiotic/bacterial infection	
Lithium	Anti-mania/bipolar disorder	
Mirtazapine	Anti-depressant	
Moexipril/HCTZ	Anti-hypertensive/high blood pressure	
Nicardipine	Anti-hypertensive/high blood pressure	
Nilotinib	Anti-cancer/Leukemia	
Octreotide	Endocrine/acromegaly, carcinoid diarrhea	
Ofloxacin	Antibiotic/bacterial infection	
Olanzapine	Anti-psychotic, atypical/Schizophrenia, bipolar	Combo with fluoxetine: Symbyax
Ondansetron	Anti-emetic/nausea and vomiting	
Oxytocin	Oxytocic/Labor stimulation	
Paliperidone	Antipsychotic, atypical/Schizophrenia	
Perflutren lipid microspheres	Imaging contrast agent/Echocardiography	
Quetiapine	Anti-psychotic/schizophrenia	
Ranolazine	Anti-anginal/chronic angina	
Risperidone	Anti-psychotic/schizophrenia	

Roxithromycin	Antibiotic/bacterial infection	
Sertindole	Antipsychotic, atypical/Anxiety, Schizophrenia	
Sunitinib	Anti-cancer/RCC, GIST	
Drug (Generic Names)	Drug Class (Clinical Usage)	Comments
Tacrolimus	Immunosuppressant/Immune suppression	
Tamoxifen	Anti-cancer/breast cancer	
Telithromycin	Antibiotic/bacterial infection	
Tizanidine	Muscle relaxant	
Vardenafil	Phosphodiesterase inhibitor/vasodilator	
Venlafaxine	Anti-depressant/depression	
Voriconazole	Anti-fungal/anti-fungal	
Ziprasidone	Anti-psychotic/schizophrenia	

Source: [www.QTdrugs.org/](http://www.QTdrugs.org/)

VEROnA

A window of opportunity study of vandetanib-eluting radiopaque beads (BTG-002814) in patients with resectable liver malignancies

Protocol Number:	BTG-002814-01
------------------	---------------

STATISTICAL ANALYSIS PLAN

Date finalised	16 May 2019
Version number	1.0
Prepared by	[name], [name], [name]

Signed: [name]

Contents

1. Summary description of the trial
2. Baseline characteristics
3. Administration of BTG-002814
4. Primary endpoints (adverse events and plasma/tissue drug concentrations)
5. Secondary endpoints
6. Tumour pathology of the surgical resection
7. Additional treatments
8. Follow up and deaths

1. Summary description of the trial

Sample size	A target of 12 patients
Intervention arms (what treatments were given)	BTG-002814 (vandetanib-eluting radiopaque embolic beads), given 7-21 days before surgery.
Primary trial objectives	Primary objectives: 
• To assess the safety and tolerability of treatment with BTG-002814• Measure the plasma and resected liver tissue concentrations of vandetanib and the N-desmethyl metabolite following treatment with BTG-002814
Primary outcome measures	
• Adverse events (AEs) related to treatment with BTG-002814 using the standardised grading criteria (National Cancer Institute- Common Terminology Criteria for Adverse Events- Version 4.0 (NCI-CTCAE v4.0))• Concentration of vandetanib and N-desmethyl vandetanib in plasma and in resected liver tissue following treatment with BTG-002814.

[figure not shown]
SAP developed according to protocol version 6, 03 December 2018

The analyses will be performed using SAS (likely version 9.4).

Missing data in the analyses below will be indicated as such in tables (there will be no imputation).

Secondary objectives

 • Evaluate the anatomical distribution of BTG-002814 on non-contrast enhanced imaging using 4D CT • Evaluate histopathological features in the surgical specimen following treatment with BTG-002814 • Assess changes in blood flow on dynamic contrast-enhanced magnetic resonance imaging (DCE-MRI) following treatment with BTG-002814
Secondary outcomes measure

 • Distribution of BTG-002814 on non-contrast enhanced imaging of tumour vasculature and regions of interest using 4D CT • Evaluation of histopathological features in the surgical specimen (malignant and non-malignant liver tissue): tumour necrosis, viable tumour, vascular changes • Changes in blood flow on DCE-MRI following treatment with BTG-002814. The following parameters will be derived from DCE-MRI images: K_{trans}, K_{ep} and V_e
Exploratory Objectives and Outcomes

 • Study blood biomarkers with the potential to identify patients likely to respond to treatment with BTG-002814 • Study tissue biomarkers to explore key immune, inflammatory and drug related mechanisms • Correlate the distribution of BTG-002814 on imaging with pathology by 3D modelling

Study Schema

2. Baseline characteristics

Table showing the number of patients (categorical variables) or the mean/median and range (for continuous variables), for:

- Gender, age, ethnicity, ECOG performance status.
- HCC or colorectal cancer
- For HCC, state whether histological or radiological diagnosis
- Location (liver segments) and characteristics of the tumour: number of liver lesions, sum of longest diameters (mm).
- Vital signs: blood pressure, weight, height, heart rate, ECG results (including QTc interval)
- Key baseline laboratory measures: Hemoglobin, absolute neutrophil count, platelets, serum bilirubin, serum creatinine, liver function tests, and others agreed by the investigators (from the screening case report form Visit 0).
- Child-Pugh score and serum alpha-fetoprotein level (HCC patients only)
- Tumour markers (colorectal cancer patients only): CEA, CA19-9, CA125
- Previous systemic treatments for cancer

Provide in the text or CONSORT diagram:

- The number of patients who were ineligible, and the reasons why they were ineligible
- The number of patients who were recruited to the trial but withdrew later on, and the reasons (if available)
- List any possible major protocol violations or ineligibility criteria that would lead to the patient not being included in the analysis. This information is not in the main database but would be summarised in a table.

3. BTG-002814 treatment

Assessments on treatment day

Measurements	Mean/median, and range, and standard deviation
Before BTG-002814 treatment (absolute values)	
Blood pressure	
Heart rate	
ECG QTc interval (state method used for calculation)	
ECG results (descriptive)	
After BTG-002814 treatment (but use the change/difference from the pre-treatment levels)	
Blood pressure	
Heart rate	
ECG QTc interval	
ECG results (descriptive)	

Delivery of BTG-002814

Measurements	
Volume of drug delivered (mL)	Mean/median, and range
Full volume of drug delivered: yes or no	Percentage
Full volume of drug not delivered- reasons	Percentages
Stasis reached	
Complication	
State other reasons	
Total time between start of 1 st infusion and end of the last infusion (minutes)	Mean/median, and range
Number of infusions over all patients	Mean/median, and range
Radiation dose-length product (mGy-cm)	Mean/median, and range
Any TACE-related problems: yes or no	Percentage
Different TACE-related problems	Percentages

4. Primary endpoints

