## 4.5. Study Endpoints

### 4.5.1. Co-Primary Endpoints

- Adverse events (AEs) related to treatment with BTG-002814 using the standardised grading criteria (National Cancer Institute Common Terminology Criteria for Adverse Events Version 4.0 (NCI-CTCAE v4.0))
- Concentration of vandetanib and N-desmethyl vandetanib in plasma and in resected liver tissue following treatment with BTG-002814.

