### 9.2.1. Analysis Populations and Sub-Groups

The Analysis Population will consist of all patients who received treatment with BTG-002814. The safety and efficacy analyses will be performed on the Analysis Population. Results will be presented separately for HCC and mCRC patients.

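### SAP section 2 allows a patient to be left out of the analysis for major violations or ineligibility, which does not fit the all-treated population in Protocol 9.2.1

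*SAP*

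**What the plan says.** Protocol 9.2.1 defines one population: "The Analysis Population will consist of all patients who received treatment with BTG-002814". It then fixes its use: "The safety and efficacy analyses will be performed on the Analysis Population". Under that rule the only ground for being left out is not having been treated.

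SAP section 2 (Baseline characteristics) ends with items to be given in the text or a CONSORT diagram. After the counts of ineligible and withdrawn patients comes: "List any possible major protocol violations or ineligibility criteria that would lead to the patient not being included in the analysis". It continues: "This information is not in the main database but would be summarised in a table".

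The SAP ties itself to the current protocol: "SAP developed according to protocol version 6, 03 December 2018". It does not repeat the all-treated definition, and SAP 4.1, which sets out the adverse event tables, gives no population or denominator.

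One co-primary endpoint in Protocol 4.5.1 is "Adverse events (AEs) related to treatment with BTG-002814 using the standardised grading criteria". Protocol 9.5.1 asks for it as numbers and percentages of patients, so the denominator matters.

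**The concern.** The SAP is what the programmer will follow. Its only remark about who is in or out of the analysis presupposes grounds for exclusion that the Protocol does not contain. Both documents refer to the same protocol version, so a version difference cannot explain the mismatch.

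At stake is the co-primary safety result of a first-in-human, open-label study with a target of 12 patients, 6 per disease. A patient treated in breach of an eligibility criterion may be one whose tolerability is of particular interest. For example, exclusion criterion 3 concerns QTc and QT-prolonging medicines, Protocol 8.1.8 describes QT prolongation with vandetanib, and QTc prolongation is a row in the SAP's adverse event table. If such a patient were treated and then left out, the tables would no longer describe everyone exposed. The SAP gives no rule, timing or decision-maker for such an exclusion.

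**Working it through.** **Planned numbers.** Protocol 9.1 gives 3 patients in the first stage and 9 more after the safety review: 3 + 9 = 12 = 6 HCC + 6 mCRC. With up to 2 replacements, 12 + 2 = 14. Both stated figures reproduce. The study is not powered, so no power formula applies.

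**The texts side by side.**

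| Question | Protocol 9.2.1 | SAP section 2 |
|---|---|---|
| Who is analysed? | Everyone treated | Not defined |
| Ground for leaving a patient out | Not treated | Major violation or ineligibility |
| Limited to untreated patients? | Yes, by definition | Not stated |
| Is safety exempt? | Safety uses the same population | Not stated |

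Protocol 11.9.1 counts as major "Enrollment violations: eligibility criteria deviations, informed consent issues" but attaches no exclusion from analysis to them. Replacing a patient (Protocol 5.5 and 9.1) does not take a treated patient out of the Analysis Population either.

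**What one exclusion does.** The event counts below are assumptions, since the documents give none. Suppose x of n treated patients have a given toxicity and one of the x is left out. The rate goes from x/n to (x − 1)/(n − 1). Exact (Clopper-Pearson) 95% limits are the Beta quantiles B(0.025; x, n − x + 1) and B(0.975; x + 1, n − x). For x = 0 the lower limit is 0 and the upper limit is 1 − 0.025^(1/n).

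| Setting | All treated | One affected patient left out |
|---|---|---|
| Whole study, one case | 1/12 = 8.3% (0.2% to 38.5%) | 0/11 = 0% (0% to 28.5%) |
| Whole study, two cases | 2/12 = 16.7% (2.1% to 48.4%) | 1/11 = 9.1% (0.2% to 41.3%) |
| One disease, one case | 1/6 = 16.7% (0.4% to 64.1%) | 0/5 = 0% (0% to 52.2%) |
| Maximum size, one case | 1/14 = 7.1% (0.2% to 33.9%) | 0/13 = 0% (0% to 24.7%) |

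For example, the upper limit for 0/11 is 1 − 0.025^(1/11) = 28.5%.

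**Is the smaller n the problem?** At an assumed true rate of 10%, the chance of at least one case is 1 − 0.9^12 = 71.8% with 12 patients and 1 − 0.9^11 = 68.6% with 11. The loss from one fewer patient is small. The distortion comes from losing a patient who had the event.

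**The case against.** The strongest reply is that the SAP line is a reporting instruction and not an exclusion rule. It sits in a patient-flow list, refers to possible violations, and speaks of the patient without saying whether that patient was treated. A reading that agrees with the Protocol exists. Registration comes before treatment, the baseline visit follows registration, and arteriography precedes bead delivery, so a registered patient can be found ineligible and never treated. That patient is outside the Analysis Population anyway, and the bullet would explain why.

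This stands for some ineligible patients. It does not naturally account for major protocol violations: an untreated patient is out because of not being treated, and no violation is needed.

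It is also fair that SAP 4.1 pools adverse events from every source and includes a table covering the whole period from delivery of treatment. But that concerns which events are collected and does not settle which patients are counted. Protocol 9.5.1 lists deaths, serious events and withdrawals due to adverse events separately, and the Safety Committee reviews all adverse events. An excluded patient's events would therefore probably still be seen somewhere. The exposure is in the summary tables.

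Two stronger readings are tempting. First, because major deviations in Protocol 11.9.1 include "Data violations: those affecting primary study endpoints", a reader might infer that exclusion could turn on the outcome itself. The documents do not support this. That section links no deviation to exclusion, its natural sense is a failure of conduct that compromises endpoint data, and having an adverse event is not a deviation. The SAP also speaks of violations and the Protocol of deviations, so even the link between the two is inferred. Second, a reader might infer concealment because the information is held outside the main database. The same SAP sentence says that it will be tabulated, so an exclusion would be disclosed.

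**Conclusion.** The inconsistency holds and should be corrected before the analysis. The Protocol puts every treated patient in the safety and efficacy analyses. The SAP's only statement on inclusion contemplates removal on other grounds, without limiting it to untreated patients and without exempting safety, and nothing else in the SAP overrides it.

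The claim is about what the wording permits. The documents do not show that the sponsor plans to drop treated patients, since "treated" is a literal reading of an unrestricted sentence.

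The size is conditional. It needs a treated patient who is a major violator or ineligible, who has the toxicity, and who is then left out contrary to Protocol 9.2.1. In that case one exclusion can remove an event from the table altogether (8.3% to 0% overall, 16.7% to 0% within one disease) or roughly halve its rate (16.7% to 9.1%). The intervals are wide and overlap heavily, the study is descriptive, and the counts are illustrative.

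**What to change.** Replace the SAP section 2 instruction with wording such as:

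> Every patient given any BTG-002814 is included in all safety and efficacy analyses (Protocol 9.2.1). Major deviations and ineligibility are listed but do not remove a treated patient. Individual PK or imaging data points that cannot be used are flagged with the reason. Patients registered but not treated appear only in the flow diagram.

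If a reduced set is wanted, for example for PK, it should be named, defined in advance and presented only as a supplement.

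The cost is a wording change in the SAP. The sample size (12, maximum 14), data collection, Protocol and patient care are unaffected. If exclusion of treated patients was never intended, the change only makes that plain. Part of the content is already planned: the SAP marks missing data without imputation (section 1) and asks for technical reasons for missing tissue data points (4.2.2).
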